5.2 EXCLUSION CRITERIA

An individual who meets any of the following criteria will be excluded from participation in this study:

1. Current or recent (within 4 weeks) treatment with any corticosteroids; however, high-dose inhaled steroids, which are used to treat acute or chronic bronchial inflammation, will be permitted
2. Current or recent (within 4 weeks) treatment with any antivirals
3. Room air oxygen saturation (SaO_2) $< 94\%$ at screen
4. Walking oximetry $< 90\%$ or participant unable to complete 6-minute walking oximetry test at screen
5. Severe Covid-19 symptoms (severe per FDA classification – see appendix 3)
6. Requires immediate admission to hospital for any reason
7. Pregnancy or lactation
8. Known allergic reactions to components of black seed oil, or thymoquinone
9. Treatment with another investigational drug or other investigational intervention within 2 weeks of study start and throughout study duration.
10. Significant hepatic disease ($\text{ALT}/\text{AST} > 4$ times the ULN); any laboratory parameter ≥ 4 times the ULN
11. History of severe chronic kidney disease or history of liver disease

12. Patients with inflammatory bowel disease (such as Crohn's) that could affect the intestinal absorption of TQ Formula enteric coated capsules.
13. Known HIV or Hepatitis C infection
14. Influenza diagnosis (confirmed by testing) during screening or within prior 14 days
15. Any uncontrolled condition(s) or diagnosis, both physical or psychological, or physical exam finding that precludes participation, as per investigator

5.3 LIFESTYLE CONSIDERATIONS

It is recommended that doses be taken with food, approximately 12 hours apart. Participants may continue with their normal standard of care, including any supplements or vitamins.

5.4 SCREEN FAILURES

Screen failures are defined as participants who consent to participate in the clinical trial but are not subsequently randomly assigned to the study intervention or entered in the study. A minimal set of screen failure information is required to ensure transparent reporting of screen failure participants, to meet the Consolidated Standards of Reporting Trials (CONSORT) publishing requirements and to respond to queries from regulatory authorities. Minimal information includes demography, screen failure details, eligibility criteria, and any serious adverse event (SAE).

Individuals who do not meet the criteria for participation in this trial (screen failure) because of an initial negative Covid-19 test may be rescreened. Rescreened participants should be assigned a new participant number, with a source note indicating that the participant is being re-screened.

5.5 STRATEGIES FOR RECRUITMENT AND RETENTION

Participants will be identified through Covid-19 screening tests at participating study sites and potential referral centers. Individuals who test positive for Covid-19 will be contacted and asked if they wish to participate in a research study. Upon signing of the informed consent, each patient will undergo screening procedures to determine eligibility for the study. Each study site may develop a site-specific recruitment plan if required.

Up to 60 participants will be equally randomized to receive either TQ Formula 3g (3x 500 mg capsules, BID) or matching placebo capsules (See section 9.2 for sample size determination details). There will be between 2-4 US sites participating in this study. The sites will be outpatient clinics that are currently testing/treating Covid-19 patients.

It is anticipated that each site will recruit approximately 4-5 participants per week. Based on this anticipated accrual rate, 2 sites should be able to complete recruitment for this study within approximately 4-5 weeks.

Participants will be compensated a reasonable amount for their study time and out of pocket costs such as parking, transportation or food on visit days will be reimbursed.

6 STUDY INTERVENTION

6.1 STUDY INTERVENTION(S) ADMINISTRATION

6.1.1 STUDY INTERVENTION DESCRIPTION

The study intervention is TQ Formula capsules, 500 mg per capsule. The control product is placebo capsules, identical in appearance to TQ Formula capsules but with no active ingredients.

Black seed oil is currently available as a food supplement, with 500 mg capsules being sold over the counter. For the purposes of this trial, both TQ Formula and placebo capsules will be manufactured as over-encapsulated capsules. A specific batch and lot will be produced, with appropriate stability testing.

6.1.2 DOSING AND ADMINISTRATION

All study participants will receive the same dose of either TQ Formula (total dosing of 3 g per day) or placebo for the duration of the study. Study participants should take 3 capsules orally (500 mg each), approximately 12 hours apart, two times per day (BID). Each dose should be taken preferably with food. Missed doses will not be made up; however, the window for dosing is +/- 6 hours. If longer than 6 hours since missed dose, participants should continue with next scheduled dose. There are no dose limiting effects anticipated with this investigational drug.

6.2 PREPARATION/HANDLING/STORAGE/ACCOUNTABILITY

6.2.1 ACQUISITION AND ACCOUNTABILITY

A central IP depot will provide the pre-labelled, pre-packaged investigational product to the study sites. Sites will receive an initial shipment and possibly a second shipment (if required). All used, unused and/or expired product will be returned to the IP depot or destroyed onsite if study site meets regulatory requirements for destruction and can provide appropriate documentation for sponsor.

6.2.2 FORMULATION, APPEARANCE, PACKAGING, AND LABELING

The investigational drug consists of 500 mg of black seed oil per capsule. Placebo consists of similar oil without active ingredient. Investigational drug will be undistinguishable from placebo; the appearance of the capsules and all packaging will be identical. Investigational product will be packaged as 500 mg/placebo capsules; each participant will receive a total of 84 capsules in order to take 6 capsules per day for the 14-day study treatment period. Investigational product will be labelled per CFR regulations.

6.2.3 PRODUCT STORAGE AND STABILITY

Both study and placebo product capsules should be stored at ambient temperature (15°C to 25°C) and protected from sunlight exposure. Investigational product should be stored in a locked, limited-access room. Only designated study personnel should dispense investigational product.

6.2.4 PREPARATION

There is no preparation of study or placebo product required by the study site. All pre-packaged and pre-labelled kits with appropriate number of capsules for 14 days of dosing for each patient are provided to the sites. Sites will be provided with a randomization number for each subject that will correspond to a kit number on site.

6.3 MEASURES TO MINIMIZE BIAS: RANDOMIZATION AND BLINDING

Study participants will be randomized in a one to one fashion (1:1) to receive either 3 g/day of TQ Formula (500 mg capsules x 3, BID) or placebo capsules (identical in appearance to active product) for 14 days. Participants will receive the full study supply (14-day medication) at randomization. Study capsules should be stored at ambient temperature (15°C to 25°C), away from direct sunlight.

The study is double blinded; all subjects, investigators, and study personnel involved in the conduct of the study, including data management and primary biostatistician, will be blinded to treatment assignment. There will be an independent unblinded statistician. The unblinded study statistician will not otherwise participate in study procedures or data analysis.

A randomization list will be prepared by the unblinded statistician and provided to the investigational product (IP) depot for labelling. Sponsor and CRO study staff will remain blinded to study treatment. Randomization numbers will be assigned through the Electronic Data Capture (EDC) system.

Participants will complete a daily questionnaire on Covid-19 symptoms, which will be used to determine the primary endpoint for the study. For this reason, it is important that participants remain blinded to treatment allocation. Participants will, however, have access to their viral test results after Day 14, if a test is completed as part of standard of care.

Unblinding

In the unlikely event that unblinding is required, the principal investigator can contact the unblinded statistician to unblind treatment. Treatment unblinding is discouraged if knowledge of the treatment assignment will not materially change the planned management of a medical emergency.

Unblinding should be discussed in advance with the medical monitor if possible. If the investigator is not able to discuss treatment unblinding in advance, then he/she must notify the medical monitor as soon as possible about the unblinding incident without revealing the participant's treatment assignment.

6.4 STUDY INTERVENTION COMPLIANCE

Investigators will assess compliance to study treatment dosing during each visit with participants. In addition, participants will be asked to return all investigational product with them to each on-site visit for compliance verification. Investigator or designee will perform IP accountability and document on appropriate study logs and source documentation on site. Patient compliance must remain between 80% and 120% throughout the course of the study. Patients who miss more than 6 consecutive doses will be labelled as non-compliant and will not be included in the per protocol population. These patients will be included in the safety analyses.

6.5 CONCOMITANT AND PROHIBITED THERAPY

For this protocol, a prescription medication is defined as a medication that can be prescribed only by a properly authorized/licensed clinician. Medications to be reported in the Electronic Case Report Form (eCRF) are concomitant prescription medications, over-the-counter medications and supplements.

Concomitant medication usage will be collected at screening and throughout the course of the study at each study visit. Any medication currently being taken at the time of screening will be recorded at the screening visit. Any changes in concomitant medication usage will be documented throughout the course of the study during study visits.

All standard of care medication to treat Covid-19 is allowed per investigator discretion.

Prohibited Medications

All standard of care medication is allowed during the course of the clinical trial. The use of any drugs approved to treat severe Covid-19 requiring hospitalization, such as: corticosteroids, antivirals, Hydroxychloroquine is prohibited for entry into the study. The use of these medications is considered inpatient regimen for severe Covid-19, and these patients are excluded from this trial. If any participant requires these medications due to worsening of Covid-19 symptoms, study treatment will be stopped and participant will continue to be followed for safety (See Appendix 4).

Investigators should carefully assess patients who are currently being treated with any drugs that are metabolized by CYP2C9 due to potential for interaction with Thymoquinone (See Appendix 5).

6.5.1 RESCUE MEDICINE

This section is not applicable.

7 STUDY INTERVENTION DISCONTINUATION AND PARTICIPANT DISCONTINUATION/WITHDRAWAL

7.1 DISCONTINUATION OF STUDY INTERVENTION

Discontinuation of investigational product does not mean discontinuation from the study, and remaining study procedures should be completed as indicated by the study protocol. If a clinically significant finding is identified (including, but not limited to changes from baseline) after enrollment, the investigator or qualified designee will determine if any change in participant management is needed. Any new clinically relevant finding will be reported as an adverse event (AE).

The data to be collected at the time of study intervention discontinuation will include the following:

- Reason for discontinuation
- Adverse events
- Changes to concomitant medications

If a participant discontinues investigational product, all study visits will continue as per the Schedule of Assessments (SOA).

Participants who are randomized but who subsequently have a negative RT-PCR Covid-19 test, will discontinue investigational product, but will continue to be followed up for safety and efficacy.

7.2 PARTICIPANT TREATMENT DISCONTINUATION/WITHDRAWAL FROM THE STUDY

Participants are free to withdraw from participation in the study at any time upon request.

An investigator may discontinue or withdraw a participant from the study treatment for the following reasons:

- Pregnancy
- Significant study intervention non-compliance
- If any clinical adverse event (AE), laboratory abnormality, or other medical condition or situation occurs such that continued participation in the study would not be in the best interest of the participant
- Disease progression which requires discontinuation of the study intervention
- If the participant meets an exclusion criterion (either newly developed or not previously recognized) that precludes further study participation

The reason for participant treatment discontinuation or withdrawal from the study will be recorded in the source documents and on the Electronic Case Report Form (eCRF).

For any participants who withdraw from the study, all attempts should be made to ensure that a safety follow up visit is completed (Day 21 procedures).

7.3 LOST TO FOLLOW-UP

A participant will be considered lost to follow-up if he or she fails to attend 3 consecutive scheduled visits (either telehealth or in person) and is unable to be contacted by the study site staff.

The following actions must be taken if a participant fails to return to the clinic for a required study visit:

- The site will attempt to contact the participant and reschedule the missed visit within 1 day and counsel the participant on the importance of maintaining the assigned visit schedule and ascertain if the participant wishes to and/or should continue in the study.
- Before a participant is deemed lost to follow-up, the investigator or designee will make every effort to regain contact with the participant (where possible, 3 telephone calls and, if necessary, a certified letter to the participant's last known mailing address or local equivalent methods). These contact attempts should be documented in the participant's medical record or study file.
- Should the participant continue to be unreachable, he or she will be considered to have withdrawn from the study with a primary reason of lost to follow-up.

8 STUDY ASSESSMENTS AND PROCEDURES

Administrative Procedures
Informed consent
Inclusion/exclusion criteria
Demographics and medical history
Prior and concomitant medication review
Randomization and Study intervention
Modified FLU-PRO Plus Questionnaire
Complete case report forms
Clinical Procedures/Assessments
Review adverse events and concomitant medications
Physical examination
Height, weight, and vital signs (T, P, RR, BP)
Pulse and Walking Oximetry
LOCAL Laboratory Assessments
Covid-19 Rapid Antigen Test
Pregnancy test (only for females of child-bearing potential)
Hematology (CBC with differential)
Chemistry panel
CENTRAL Laboratory Assessments
RT-PCR sample for quantitative viral load analysis
Whole blood for biomarker/immune studies (serum and plasma)

8.1 EFFICACY ASSESSMENTS

Covid-19 Quantitative Viral Load (RT-PCR)

Participants will have an RT-PCR sample taken at baseline, day 7 and day 14 to measure quantitative viral load and viral load clearance. These samples will be sent to a central laboratory for analysis.

Patient Reported Outcomes

Participants will receive the Modified FLU-PRO Plus questionnaire (Appendix 2) to complete on a daily basis for the duration of the study, from randomization to final study visit. The responses will be used to measure severity and change in Covid-19 symptoms from baseline.

Serum Collection (Blood sample for immune monitoring)

Participants will have blood collected for immune monitoring. This testing will explore pharmacokinetics and inflammatory cytokines, coagulation factors and effector immune cells in samples. These samples will be sent to a central laboratory for analysis.

8.2 SAFETY AND OTHER ASSESSMENTS**Physical Exam**

A complete physical exam of the following systems will be performed by the investigator or appropriately qualified designee and documented in the source and in the eCRF at Screening, Day 7 and Day 14. A complete physical examination, performed at screening and other specified visits, should include an evaluation of the head, eyes, ears, nose, and throat, and the cardiovascular, dermatologic, respiratory, gastrointestinal, and neurologic systems.

Vital Signs

Vital signs, including blood pressure (BP), temperature, respiratory rate and heart rate will be collected throughout the course of the study.

Laboratory Evaluations (Hematology and Serum Chemistry)

The following laboratory evaluations will be tested locally at screening, Day 7 and Day 14: Albumin, total protein, alkaline phosphatase, total bilirubin, direct bilirubin, ALT, AST, sodium, potassium, chloride, bicarbonate, BUN, creatinine, phosphorus, calcium, glucose, CBC/diff, LDH, CRP, prothrombin time, activated partial prothrombin time, D-dimer. In the event of elevated liver enzymes, please see section 8.5 for the drug induced liver injury plan.

Adverse Event Review and Evaluation

Participants will be assessed for any new adverse events throughout the course of the study. Participants will be encouraged to contact the study site immediately if they observe any worsening symptoms or health concerns.

8.3 ADVERSE EVENTS AND SERIOUS ADVERSE EVENTS

8.3.1 DEFINITION OF ADVERSE EVENTS (AE)

Adverse event is defined as any untoward medical occurrence associated with the use of an intervention in humans, whether or not considered intervention-related (21 CFR 312.32 (a)).

For this study, adverse events will be captured from the time of informed consent until 7 days after last dose of investigational product (30 days after last dose for SAEs)

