1.2 SCHEMA

1.3 SCHEDULE OF ACTIVITIES (SOA)

Procedures	Screen Visit	Baseline ^d Visit	Study Visit 2 ^f	Study Visit 3 ^g	Study Visit 4 ^f	Study Visit 5 ^g	Final Study Visit ^f	Safety Follow Up Phone Call
	Day -3 to -1	Visit 1, Day 1	Day 4 +/- 1 day	Day 7 +/- 1 day	Day 10 +/- 1 day	Day 14 +/- 1 day	Day 21 +/- 1 day	Day 45 +/- 1 day
Informed consent	X							
Demographics	X							
Medical history	X							
Inclusion/Exclusion Criteria Evaluation	X	X						
Rapid Antigen Test for Covid-19	X ^c							
RT-PCR sample for quantitative viral load analysis		X ^c		X		X		
Serum Collection (Blood sample for immune monitoring)		X		X		X		
Physical exam	X			X		X		
Vital signs	X	X		X		X		
Pulse Oximetry	X							
Walking Oximetry	X							
Height	X							
Weight	X							
Hematology	X		X ^e	X	X ^e	X		
Serum chemistry ^a	X		X ^e	X	X ^e	X		
Pregnancy test ^b	X							
Randomization		X						
Administer study intervention		X.....X						
Concomitant medication review	X	X	X	X	X	X	X	
Adverse event review/evaluation	X	X	X	X	X	X	X	X
Patient Reported Outcomes (Modified FLU-PRO Plus)*	X*	X.....X						
Complete Case Report Forms (CRFs)	X	X	X	X	X	X	X	

a: Albumin, alkaline phosphatase, total bilirubin, direct bilirubin, bicarbonate, BUN, calcium, chloride, creatinine, glucose, LDH, phosphorus, potassium, total protein, AST, ALT, sodium, CBC/diff, LDH, , CRP, prothrombin time, activated partial prothrombin time, , D-dimer b: Serum pregnancy test (women of childbearing potential).

c: Covid-19 Confirmatory test in addition to quantitative viral load

d: Screening and Baseline can be combined

e: If clinically indicated at the discretion of the investigator

f: Visits at Day 4 (visit 2), Day 10 (visit 4), and Day 21 (final visit) will be telehealth and can be changed to in-person at the discretion of the investigator g: In the event of a complete lockdown due to Covid, visits at Day 7(Visit 3) and Day 14 (Visit 5) could be replaced by home health visit for sample collection and telehealth visit for clinical evaluation.

*Administered everyday

+ Modified FLU-PRO Plus at Screen will be completed on site to determine if patient meets inclusion criterion

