8.3.2 DEFINITION OF SERIOUS ADVERSE EVENTS (SAE)

An adverse event (AE) or suspected adverse reaction is considered "serious" if, in the view of either the investigator or sponsor, it results in any of the following outcomes:

- Death
- A life-threatening adverse event
- Inpatient hospitalization or prolongation of existing hospitalization
- A persistent or significant incapacity or substantial disruption of the ability to conduct normal life functions, or
- A congenital anomaly/birth defect

Important medical events that may not result in death, be life-threatening, or require hospitalization may be considered serious when, based upon appropriate medical judgment, they may jeopardize the participant and may require medical or surgical intervention to prevent one of the outcomes listed in this definition. Examples of such medical events include allergic bronchospasm requiring intensive treatment in an emergency room or at home, blood dyscrasias or convulsions that do not result in inpatient hospitalization, or the development of drug dependency or drug abuse.

SAEs will be captured from the time of informed consent until 30 days after the last dose of investigational product. For information on SAE reporting and associated procedures and forms, refer to the study Safety Plan.

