8.3.4 TIME PERIOD AND FREQUENCY FOR EVENT ASSESSMENT AND FOLLOW-UP

The occurrence of an adverse event (AE) or serious adverse event (SAE) may come to the attention of study personnel during study visits and interviews of a study participant presenting for medical care, or upon review by a study monitor.

All AEs including local and systemic reactions not meeting the criteria for SAEs will be captured on the appropriate electronic case report form (eCRF). Information to be collected includes event description, time of onset, clinician's assessment of severity, relationship to study product (assessed only by those with the training and authority to make a diagnosis), and time of resolution/stabilization of the event. All AEs occurring while on study must be documented appropriately regardless of relationship. All AEs will be followed to adequate resolution.

Any medical condition that is present at the time that the participant is screened will be considered as baseline medical history and not reported as an AE. However, if the study participant's condition deteriorates at any time during the study, it will be recorded as a new AE.

Changes in the severity of an AE will be documented to allow an assessment of the duration of the event at each level of severity to be performed. AEs characterized as intermittent require documentation of onset, severity, and duration of each episode.

The principal investigator or designee will record all reportable events with start dates occurring any time after informed consent is obtained until 7 (for non-serious AEs) or 30 days (for SAEs) after the last dose of study drug. At each study visit, the investigator will inquire about the occurrence of AE/SAEs since the last visit. Events will be followed for outcome information until resolution or stabilization. A final follow-up phone call will be performed at Day 45 in order to assess status of any ongoing AEs or SAEs. Any AEs that are considered unresolved at Day 45 will be followed clinically by the investigator until resolution or stabilization.

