# BOSS-Covid-19 Study (BOSS-001)

taking placebo. All AEs/SAEs will be captured throughout the study as per schedule of assessments.

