Primary Estimand-2 for the safety objective is the difference of frequencies of Adverse Events and Serious Adverse Events between participants taking 3 g TQ Formula (500 mg per capsule, 3 capsules BID) and participants taking placebo regardless of whether or not they actually receive their assigned therapy (ITT) and assuming that their hospitalization and treatment discontinuation rates will be similar. The above mentioned intercurrent events are also applicable for this safety estimand. Therefore, hospitalization-free, while-on-study and per-protocol treatment versions of the above estimand will also be considered within each population definitions above.

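### The protocol gives two conflicting adverse-event recording windows, and one of them closes early for participants who stop treatment early

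*Protocol*

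**What the plan says.** Two rules stand side by side.

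**Last-dose rule.** Protocol 8.3.1: "adverse events will be captured from the time of informed consent until 7 days after last dose of investigational product". Protocol 8.3.2: "SAEs will be captured from the time of informed consent until 30 days after the last dose of investigational product". Protocol 8.3.4 turns both into the recording instruction, applied to event start dates: "until 7 (for non-serious AEs) or 30 days (for SAEs) after the last dose of study drug".

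**Throughout-study rule.** Protocol 8.3.4 also says: "All AEs occurring while on study must be documented appropriately regardless of relationship". The safety endpoint in SAP 4.2 reads: "All AEs/SAEs will be captured throughout the study as per schedule of assessments". The same endpoint wording is in the protocol synopsis, Section 3 and Section 9.1. Protocol 8.2 has participants assessed for new events over the whole course of the study. In the Schedule of Activities (1.3), the row "Adverse event review/evaluation" is marked at every contact from screening to the Day 45 call. Protocol 7.1 keeps participants who stop study product on the full visit schedule.

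**Analysis.** Protocol 9.4.3 tabulates episodes over number of subjects and compares percentages of patients with an AE, or a set of AEs, by Fisher's exact test. SAP 5.3.6 mentions incidence rates but defines no time denominator. The safety estimand in SAP 5.3.2 compares the arms regardless of treatment received and assumes that discontinuation rates will be similar. Safety is the second primary objective in SAP 3.6.

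**The concern.** Take a non-serious event that starts on Day 14 in someone whose last dose was on Day 3. Protocol 8.3.1 leaves it out and SAP 4.2 takes it in. No passage ranks one rule above the other, so sites may differ.

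If the last-dose rule is followed, the length of the recording window depends on how long the participant took the product. That fits poorly with an estimand defined regardless of treatment received. It also fits poorly with an analysis that divides by subjects and not by time at risk. Early stopping is foreseen for toxicity or an unresolved delay (Protocol 4.3), for worsening Covid-19 that needs a listed medication (6.5), for a negative RT-PCR (7.1) and for non-compliance (7.2). Toxicity and worsening disease could plausibly differ by arm. An arm with more or earlier stopping would then have fewer late-onset events on record, in a comparison that the SAP treats as primary.

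**Working it through.** **1. Windows implied by the last-dose rule.** The documents give no AE or stopping rates to reproduce, so the anchor is the completer. Dosing lasts 14 days: 14 + 7 = Day 21 and 14 + 30 = Day 44, which match the Day 21 visit and the Day 45 call. For a last dose on day d the windows close on d + 7 and d + 30.

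| Last dose | Non-serious closes | Share of 21 days | SAE closes |
|---|---|---|---|
| Day 1 | Day 8 | 38% | Day 31 |
| Day 3 | Day 10 | 48% | Day 33 |
| Day 7 | Day 14 | 67% | Day 37 |
| Day 10 | Day 17 | 81% | Day 40 |
| Day 14 | Day 21 | 100% | Day 44 |

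Everyone dosed has serious events, including hospitalisations, covered to at least Day 31. A participant who is randomised but never dosed is in the SAP's ITT set, yet has no last dose from which to count.

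**2. Effect on the percentage of patients with an AE.** Assume no true arm effect, stopping unrelated to earlier AEs, and sites that apply the last-dose rule. If the proportions stopping on day d differ by Δ, the arm that stops more is understated by

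Δ × [F(21) − F(d + 7)],

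where F(t) is the cumulative AE risk by day t and p = F(21). Assumed ranges: p from 20% to 60%, d = 3 or 7, Δ from 10 to 30 points.

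*Constant hazard*, F(t) = 1 − (1 − p)^(t/21):
- Middle case (p = 0.40, d = 3, Δ = 0.20): F(10) = 1 − 0.6^(10/21) = 0.216; 0.20 × (0.40 − 0.216) = 3.7 points, or 1.1 patients of 30.
- Lowest (p = 0.20, d = 7, Δ = 0.10): F(14) = 0.138; 0.6 points, or 0.2 patients of 30.
- Highest (p = 0.60, d = 3, Δ = 0.30): F(10) = 0.354; 7.4 points, or 2.2 patients of 30.

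*Hazard halving every 4 days*, F(t) = 1 − (1 − p)^G(t), with G(t) = (1 − 2^(−t/4)) / (1 − 2^(−21/4)): the same ranges give 0.1 to 1.8 points.

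For scale, 26 to 30 patients per arm have 80% power only for differences of about 31 to 38 points (normal approximation, comparison rate 20% to 60%).

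**3. Effect on episode counts.** With a constant event rate, expected episodes are proportional to days covered. For example, assume that 20% of one arm and 5% of the other stop on Day 3:
- 0.80 × 21 + 0.20 × 10 = 18.8 days
- 0.95 × 21 + 0.05 × 10 = 20.45 days
- ratio 0.919, about 8% fewer episodes with no true difference.

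With no stopping in the other arm, the same ranges of d and Δ give 0.10 × 7/21 = 3.3% to 0.30 × 11/21 = 15.7% fewer. If the event rate halves every 4 days, the shares of episodes starting after Days 14 and 10 are 1 − G(14) = 0.064 and 1 − G(10) = 0.155. The shortfall is then 0.10 × 0.064 = 0.6% to 0.30 × 0.155 = 4.6%.

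**The case against.** The strongest reply is that the plan does not really intend a shorter window. Text calling for capture throughout the study appears in more places than the last-dose rule, visits continue after stopping, and AE review is scheduled for everyone to Day 45. This stands in part: the documents conflict, so it is not settled that early stoppers will have fewer events recorded. But the last-dose rule is the operative instruction in the AE sections, and nothing overrides it.

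Three further points stand and limit the size.
- The rule in 8.3.4 runs on start dates, not report dates. An event that starts on Day 9 and is reported at Day 14 is recorded even after a last dose on Day 3; only onsets after Day 10 are lost.
- A participant who stops for intolerance or worsening Covid-19 will normally already have a recorded AE and so already counts in an any-AE percentage. Losses then fall on episode counts and on other AE categories, and step 2 of the working overstates the effect for such participants.
- A negative RT-PCR most naturally means the baseline confirmatory test. That reflects status before treatment and should differ by arm only by chance.

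It can also be said that the SAP states its assumption of similar discontinuation and plans while-on-study and per-protocol versions of the safety estimand. Those versions cannot recover events that were never recorded, and no method is given if the assumption fails.

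**Conclusion.** The recording window is contradictory and needs to be reconciled, whatever the size of any bias, because a site cannot follow both rules. If sites apply the last-dose rule, non-serious events that start after an early cut-off go unrecorded. The AE comparison could then be modestly biased when the amount or timing of stopping differs by arm, mainly in episode counts and specific AE categories. The actual size is unknown. Over the assumed ranges it is 0.1 to 7.4 percentage points of patients and 0.6% to 15.7% of episodes; the upper ends need a 30-point gap in stopping, every stop on Day 3 and a flat event rate. Serious events are little affected.

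A reader might infer more: that early stoppers are definitely observed for less time, and that the comparison is biased whenever stopping differs by arm. The documents do not support that. Observation continues by schedule, and bias also needs sites to apply the last-dose rule and events to start between the early cut-off and Day 21.

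**What to change.** Reconcile Protocol 8.3.1, 8.3.2 and 8.3.4 with 8.2, the Schedule of Activities and the safety endpoint text (synopsis, Section 3, Section 9.1 and SAP 4.2), using one minimum calendar recording window. It should apply to all randomised participants who remain in follow-up, whatever the date of last dose: non-serious AEs with onset to Day 21, and SAEs with onset to the Day 45 contact.

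- In 8.3.4, state that the Day 45 call also asks about new SAEs. Protocol 4.1 and 8.3.4 now describe it as a check on ongoing events.
- In SAP 5.3.6, state that the between-arm AE comparison uses onsets within this fixed window.
- Protocol 4.3 allows treatment delays of up to 10 days, and the documents do not say whether delayed doses may fall after Day 14. List any later events from delayed dosing separately, so that the comparison window stays fixed.
- Keep a last-dose-plus-7-days table as supportive.

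With the same window for everyone, the artefact in the working is zero by construction for participants who stay in follow-up. No visit is added, because AE review is already scheduled at Days 4, 7, 10, 14, 21 and 45. The cost is wording changes in both documents, a few more AE entries for early stoppers and a slightly wider Day 45 call.
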